12.5.6. Reporting of SAEs to GSK

SAE reporting to GSK via electronic data collection tool

• Primary mechanism for reporting SAEs to GSK will be the electronic data collection tool• If the electronic system is unavailable, the site will use the paper SAE data collection tool in order to report the event within 24 hours and fax it to the Medical Monitor• Site will enter the serious adverse event data into the electronic system as soon as it becomes available.• The investigator will be required to confirm review of the SAE causality by ticking the 'reviewed' box at the bottom of the Electronic case report form (eCRF) page within 72 hours of submission of the SAE.• After the study is completed at a given site, the electronic data collection tool (e.g., InForm system) will be taken off-line to prevent the entry of new data or changes to existing data• If a site receives a report of a new SAE from a study participant or receives updated data on a previously reported SAE after the electronic data collection tool has been taken off-line, the site can report this information on a paper SAE form or to the Medical Monitor or the SAE coordinator] by telephone.• Contacts for SAE receipt can be found at the beginning of this protocol on the Sponsor/Medical Monitor Contact Information page.

12.6. Appendix 6: Modified List of Highly Effective Methods of Contraception for post-menopausal females, who are taking Hormone Replacement Therapy, and Collection of Pregnancy Information

Definitions

Woman of Childbearing Potential

A woman is considered fertile following menarche and until becoming post-menopausal unless permanently sterile (see below).

Women in the following categories are not considered to be Woman of Childbearing Potential

1. Premenarchal
2. Premenopausal female with ONE of the following:
 - Documented hysterectomy
 - Documented bilateral salpingectomy
 - Documented bilateral oophorectomy
3. Postmenopausal female
 - A postmenopausal state is defined as no menses for 12 months without an alternative medical cause. A high follicle stimulating hormone (FSH) level in the postmenopausal range may be used to confirm a postmenopausal state in women not using hormonal contraception or hormonal replacement therapy (HRT). However, in the absence of 12 months of amenorrhea, a single FSH measurement is insufficient.
 - Females on HRT and whose menopausal status is in doubt will be required to use one of the non-hormonal highly effective contraception methods if they wish to continue their HRT during the study. Otherwise, they must discontinue HRT to allow confirmation of postmenopausal status before study enrollment.

Contraception Guidance

Female participants

Post-menopausal females, under 60 years of age, who are taking HRT and have not had their menopausal status confirmed, must use one of the follow methods of contraception, from dosing until the final visit.

1. Male partner sterilization with documentation of azoospermia prior to the female participant's entry into the study, and this male is the sole partner for that participant [Hatcher, 2011]. The documentation on male sterility can come from the site

personnel's: review of participant's medical records or medical history interview provided by her or her partner.

The investigator is responsible for ensuring that participants understand how to properly use these methods of contraception.

Collection of Pregnancy Information

Female Participants who become pregnant

- Investigator will collect pregnancy information on any female participant, who becomes pregnant while participating in this study
- Information will be recorded on the appropriate form and submitted to GSK within 2 weeks of learning of a participant's pregnancy.
- Participant will be followed to determine the outcome of the pregnancy. The investigator will collect follow up information on participant and neonate, which will be forwarded to GSK. Generally, follow-up will not be required for longer than 6 to 8 weeks beyond the estimated delivery date.
- Any termination of pregnancy will be reported, regardless of fetal status (presence or absence of anomalies) or indication for procedure.
- While pregnancy itself is not considered to be an AE or SAE, any pregnancy complication or elective termination of a pregnancy will be reported as an AE or SAE.
- A spontaneous abortion is always considered to be an SAE and will be reported as such.
- Any SAE occurring as a result of a post-study pregnancy which is considered reasonably related to the study treatment by the investigator, will be reported to GSK as described in [Appendix 5](#). While the investigator is not obligated to actively seek this information in former study participants, he or she may learn of an SAE through spontaneous reporting.
- Any female participant who becomes pregnant while participating will continue to attend all follow-up visits.

12.7. Appendix 7: Asthma Control Test

Country-specific, commercially available versions of the ACT will be used.

12.8. Appendix 8: Country Specific Requirements

12.8.1. Additional Hepatitis B Core Antibody test for inclusion of participants in Germany

In order to comply with German requirements for Hepatitis B virus testing in Germany, participants will be tested for the hepatitis B core antibody (anti-HBc) at screening. The German-specific exclusion criterion 5 is as follows:

Positive for **hepatitis B** surface antigen (HBsAg) and core antibody (anti-HBc) at screening.

[Table 5](#) has been updated accordingly.

12.8.2. Additional In-patient stay period for participants from Germany

In Germany, participants will remain in-patient for a minimum of 8 days post dosing, as noted in Section [4.2](#), Section [4.7.1](#), Section [7.1](#). For clarity, the time and events table for Germany is provided below.

12.8.2.1. Time and Events Table

Procedure	Pre-Screen ¹	Screen ²	In-patient Period ^{3,4}								Out-patient Visits ^{4,5}													
			Day -1	Day 1			Day 2	Day 3	Day 4	Week														
				Pre-dose	0	2 h	8 h	24 h	48 h	72 h	NA	1	NA	2	4	8	12	18	24	26	32 ⁵	36 ⁵	40 ⁵	
											5	8	9	15	29	57	85	127	169	183	225 ⁵	253 ⁵	281 ⁵	
Haematology (including blood eosinophil count), Clin. Chem., Urinalysis and hsCRP		X	X					X	X	X	X	X	X	X	X	X	X	X	X	X	X	X	X	
Serum save (for immunological analysis, if needed)		X									Ad hoc, as required by symptoms – see Appendix 3 .													
Inflammatory markers		X									Ad hoc, as required by symptoms – see Appendix 3 .													
Complement (C3 & C4)		X	X					X	X	X	X			X	X	X	X	X	X	X	X	X	X	
Total IgE			X					X	X	X	X			X	X	X	X	X	X		X	X	X	
PK Blood Samples					See Table 4 .																			
Immunogenicity				X										X	X	X	X	X	X	X	X	X	X	
CICs				X				X						X	X	X	X	X	X	X	X	X	X	
12-lead ECG ¹⁴		X	X	X		X	X	X	X	X	X	X	X	X	X	X	X	X	X	X	X	X	X	
Vital signs ¹⁵		X	X	X		X	X	X	X	X	X	X	X	X	X	X	X	X	X	X	X	X	X	
AE/SAE review (inc local ISR up to 72 h after dosing)	X ¹⁶				↔																			
IL-5 sample			X					X	X		X			X	X	X	X	X	X	X	X	X	X	
Exploratory biomarkers of asthma in blood			X												X			X						
Spirometry		X	X			X		X		X					X						X	X	X	X
PEF Training ¹⁷		X																						

Procedure	Pre-Screen ¹	Screen ²	In-patient Period ^{3,4}							Out-patient Visits ^{4,5}												
			Day -1	Day 1			Day 2	Day 3	Day 4	Week												
				Pre-dose	0	2 h	8 h	24 h	48 h	72 h	NA	1	NA	2	4	8	12	18	24	26	32 ⁵	
PEF ¹⁷																					36 ⁵	40 ⁵
Diary review ¹⁷												X	X		X	X	X	X	X	X	X	X

Abbreviations: ACT = Asthma Control Test; AE = adverse event; BMI = body mass index; CICs = circulating immune complexes; CRP = C-reactive protein; ECG = electrocardiogram; FSH = follicle stimulating hormone; h = hour(s); Hep B = Hepatitis B; Hep C = Hepatitis C; HIV = human immunodeficiency virus; IgE = immunoglobulin E; IL-5 = interleukin-5; IP = Investigational Product; ISR = injection site reactions; PEF = peak expiratory flow; PK = pharmacokinetic; SABA = short acting β -agonist; SAE = serious adverse event.

Notes:

1. Pre-screen up to 12 weeks before dosing. Blood eosinophils must be ≥ 200 cells/ μ L for participants to proceed to screening. Blood eosinophil count may be existing data or obtained at a pre-screen visit.
2. Screening up to 4 weeks before randomisation. Screening procedures may be done at one or more visits, within the screening window.
3. All participants will be in-patient for at least 8 days after dosing.
4. Allowed time deviations will be documented in the Study Reference Manual.
5. All participants will have all out-patient visits up to Week 26 after dosing. Each cohort will also have out-patient visits after week 26, depending on the dose, as follows:
 - 2 and 10 mg: Week 32 only
 - 30 mg and 100 mg: Week 36 only
 - 300 mg: Weeks 32 and 40

(For unplanned dose levels, the timing of out-patient visits will be documented in a Note to File.)

6. Informed consent will be taken either at the pre-screen visit, for participants who don't have an existing eosinophil count, or at screening, for those who do.
7. Blood eosinophils will be included in the haematology panel at all time points other than the pre-screen visit.
8. If required to confirm postmenopausal status.
9. Women on hormone replacement therapy, whose post-menopausal status cannot be confirmed, only.
10. Including cardiovascular (CV) disease, asthma exacerbation, and drug, alcohol and smoking history.
11. If the participant consents, an optional, genetic sample will be collected once during the study.
12. At each applicable visit, ACT should be done before any other assessment.
13. Height at pre-screening or screening only.
14. ECGs triplicate at all time points. ECGs should be time-matched to baseline (i.e. pre-dose on Day 1) from Day 2 onwards.
15. Blood pressure and heart rate in triplicate before dosing; single measurements after dosing. Single temperature and respiratory rate measurements at all time points.
16. Only SAEs are collected before dosing (see Section 7.3.1).

17. PEF will be recorded in the evening before bedtime on the day of the screening visit, then **twice** each day (**once in the morning upon waking and once in the evening before bedtime**) from the day after screening until the end of the study. Training of the participant in how to take measurements will occur at screening. PEF measurements will be taken and results will be recorded by the site while the participant is in-patient at the clinical site (ie from the evening of Day -1 until the morning of discharge). At all other time points, the participant will record their PEF as instructed, on their diary card, along with any rescue medication use and adverse events. Site staff will review the diary cards at each out-patient Visit.

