3. OBJECTIVES AND ENDPOINTS

Objectives	Endpoints
Primary	

 To assess the safety and tolerability of ascending single subcutaneous doses of GSK3511294 in participants with mild to moderate asthma 	
 Adverse events, serious adverse events, including systemic reactions and local injection site reactions Vital signs, ECGs, laboratory safety data – including liver and renal chemistry, high sensitivity C-reactive protein (hsCRP), and complement (C3 and C4)
Secondary	

 To evaluate the plasma pharmacokinetics of ascending single subcutaneous doses of GSK3511294 in participants with mild to moderate asthma To evaluate the dose response of blood eosinophil counts after ascending single subcutaneous doses of GSK3511294 in participants with mild to moderate asthma To assess the immunogenicity of GSK3511294 	
 Plasma pharmacokinetic parameters of GSK3511294 after single SC doses: AUC(0-∞), AUC(0-t), AUC(0-Week4), AUC(0-Week12), AUC(0-Week26), %AUCex, Cmax, tmax, tlast, CL/F, Vd/F, λz and t½ when assessable* Ratio to baseline in absolute blood eosinophil count Frequency and titers of binding ADAs to GSK3511294, before and after GSK3511294 administration
Exploratory	

 To assess the effect of single SC doses of GSK3511294 on lung function Serum total IL-5 following single SC doses of GSK3511294 To explore drug specific circulating immune complexes (CIC) after single SC doses of GSK3511294 To determine the effect of single SC doses of GSK3511294 on serum markers of asthma 	
 Change from baseline: forced expiratory volume in 1 second (FEV₁), forced vital capacity (FVC), peak expiratory flow (PEF) Serum total IL-5 levels Levels of CICs Change from baseline in asthma biomarkers

 To explore the PK/PD (blood eosinophil count) relationship after single SC doses of GSK3511294, if deemed appropriate 	
 GSK3511294 plasma concentration and blood eosinophil count for determination of Half maximal effective concentration (EC50) and maximum effect, if deemed appropriate

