4.6. Dose Justification

Pharmacokinetics: Mepolizumab and GSK3511294 plasma concentration data, generated from a single dose cynomolgus monkey PK/PD study, were modelled simultaneously along with the toxicokinetics (TK) data from the one month toxicity study, and showed that only systemic clearance differed between the two molecules. The volume of distribution of the central and peripheral compartment, as well as the inter-compartmental clearance, were similar. Clearance decreased by an estimated 1.9-fold with GSK3511294 compared to mepolizumab, and this fold reduction is expected to be preserved between monkey and human. Predicted human exposure following single GSK3511294 SC administration at the proposed doses in the study were estimated using the known mepolizumab PK in human adjusted by the predicted fold difference in clearance determined from the pre-clinical studies (Table 1 and Figure 3). Absolute bioavailability was assumed to be 75%, similar to mepolizumab. The predicted human systemic clearance (CL) is 0.00465 L/h or 0.112 L/day and the plasma elimination half-life is approximately 37 days.

IL-5 binding affinity: Due to the limitation of various *in vitro* assays, GSK3511294 binding affinity is difficult to measure, but is anticipated to be 20-30 fold more potent than mepolizumab. Simulations to reproduce the total IL-5 and blood eosinophil profiles observed in the cynomolgus monkey PK/PD study were generated using a PK/PD model developed previously based on mepolizumab pharmacology data. Whilst acknowledging the uncertainty due to the small sample size in the cynomolgus monkey study, simulations seem to support a minimum of a 30-fold higher binding affinity of GSK3511294 compared with mepolizumab.

Estimation of GSK3511294 therapeutic dose and frequency of administration: The approved mepolizumab therapeutic dose in severe eosinophilic asthma is 100 mg SC administered every 4 weeks. It is hypothesised that if the blood eosinophil reduction observed at GSK3511294 trough concentrations in steady-state conditions is similar to that observed at mepolizumab 100 mg SC trough concentrations, it is likely that similar ‘clinical efficacy’ (reduction in asthma exacerbations) to mepolizumab will also be

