	
minimal focal inflammation after administration of 100 mg/kg. Immune complex disease was not observed in the 6-month repeat dose (2 doses) study at the same doses. It is unknown whether immunogenicity in humans after dosing will result in the formation of pathogenic immune complexes as data from preclinical models is not necessarily predictive of immune complex disease in human effects.
	
low C3 or low C4), previous history of vasculitis and patients with a significantly elevated Alanine aminotransferase (ALT) or history of liver disease.
 
 ▪ Safety evaluation of individual participants will be in place, with data being reviewed on an ongoing basis by the Sponsor and Investigators. Any clinical signs that might indicate immune complex disease will be reported to the sponsor's medical monitor within 24 hours of the investigator becoming aware of the event, regardless whether the event is considered serious or non-serious. Participants will be investigated and treated as clinically indicated (Appendix 3). ▪ Targeted monitoring of laboratory data (tests shown in Section 7.3.6 and time points shown in Section 7.1) will include urinalysis to detect haematuria and microalbuminuria and clinical chemistry parameters. ADA and immune complex concentrations, trends in C3 and C4, platelets and inflammatory markers, over time will also be assessed. ▪ Halting and monitoring rules, based on the clinical findings, are defined to minimise the risk to participants (Section 5.4 and Section 5.5).

Potential Risk of Clinical Significance	Summary of Data/Rationale for Risk	Mitigation Strategy

 ▪ Immunogenicity, ADAs 	
 ▪ Biopharmaceutical products may elicit ADAs, which have the potential to modulate PK or PD, or to produce adverse reactions. This is the GSK3511294 FTIH study, hence the ADA response in humans is unknown. 	
 ▪ A single dose of GSK3511294 will be administered to a participant. ▪ Binding ADAs to GSK3511294 will be measured, and adverse event profile will be compared between ADA-positive and ADA-negative participants.

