	
spermatogenic cycle and the integrity of the various cell types present within the different stages in sexually mature males. No cell or stage specific abnormalities were noted. In addition, there is a low reproductive risk associated with the IL-5 target mechanism (as shown in pre-clinical reproductive toxicology studies of mepolizumab and reslizumab), a low genotoxic concern for mAbs in general, and a low transfer of monoclonal antibody (mAbs) into semen due to the inability of large molecular weight proteins such as GSK3511294 to access pivotal cells in the testes [Setchell, 1975; Pollanen, 1995; Pollanen, 1989; Setchell, 2001; Sohn, 2015], the risk of adverse effects on spermatogenesis is considered minimal.
	
 It is expected that spermatogenesis will not be affected by GSK3511294, so males will not be required to use contraception during the study.
Study Design		

 Duration of in-patient stay after dosing 	
 Tmax of GSK3511294 is expected at 7–10 days after dosing. However, any significant side effect of GSK3511294 in the time to Tmax is most likely to be an anaphylactic reaction, which would occur in the first 72 hours after dosing. The predicted PK profile indicates approximately 80% of Cmax at 72 hours after dosing. Participants will have a minimum 72 hour in patient monitoring period at experienced phase 1 study. 	
 In the UK, Investigators will review available safety data up to 72 hours to confirm participants are well enough to leave the clinical unit. In Germany, in response to regulatory comments, participants will be in-patient until at least 8 days after dosing. Participants will receive a medical alert card, with details of the study, clinical site and Investigator, when they are discharged from the unit. They will be instructed to

Potential Risk of Clinical Significance	Summary of Data/Rationale for Risk	Mitigation Strategy
	
Therefore, to minimise the inconvenience to participants, they may be discharged from the clinical unit 72 hours (or longer) after dosing, provided that the Investigator considers them well enough to leave.
	
contact the unit with any safety concerns they might have, and to show the medical alert card to any other medical professional they might consult.

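### The UK schedule marks C3/C4 on Day 8 and the German schedule does not, so German participants miss one scheduled sample of a primary safety measure, with no reason given

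*Protocol*

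**What the plan says.** The primary safety endpoints in Section 3 include laboratory data with "high sensitivity C-reactive protein (hsCRP), and complement (C3 and C4"). For the type III hypersensitivity risk, Section 4.7.1 says that "ADA and immune complex concentrations, trends in C3 and C4, platelets and inflammatory markers, over time will also be assessed".

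There are two schedules, Section 7.1 for the UK and Section 12.8.2.1 for Germany. Both have a row "Complement (C3 & C4"), and the German table has an extra Day 9 column. Section 12.8.2 explains the second table by the length of stay: "In Germany, participants will remain in-patient for a minimum of 8 days post dosing", and "For clarity, the time and events table for Germany is provided below". The only other German requirement in Section 12.8 is the hepatitis B core antibody test.

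On exposure, Section 4.7.1 states that "Tmax of GSK3511294 is expected at 7–10 days after dosing" and that "The predicted PK profile indicates approximately 80% of Cmax at 72 hours after dosing". Section 4.6 adds that "the plasma elimination half-life is approximately 37 days".

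**The concern.** A country appendix written to cover a longer stay should not change which safety samples are taken unless it says so. Here one complement sample present in the UK schedule is absent from the German one. German participants are in the unit on that day and blood is being drawn for other safety tests. Section 7 requires adherence to the Time and Events Table, so sites would follow the blanks.

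Two things are at stake. The first is one scheduled C3/C4 value per German participant, at a time when exposure is predicted to be reaching its peak. The second is comparability: a by-dose summary at Day 8 would be made up of UK participants only, in cohorts with 6 or 9 active and 2 or 3 placebo participants.

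**Working it through.** **Step 1. Align each row with its header.** The complement row has as many fields as its header in both tables: 23 in the UK table and 24 in the German table, counting the procedure label.

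| Row | 24 h, 48 h, 72 h | Day 5 | Day 8 | Day 9 | Day 15 and later columns |
|---|---|---|---|---|---|
| UK, C3/C4 | marked | marked | marked | no column | marked |
| Germany, C3/C4 | marked | marked | blank | blank | marked |
| UK, haematology/chemistry/urinalysis/hsCRP | marked | marked | marked | no column | marked |
| Germany, haematology/chemistry/urinalysis/hsCRP | marked | marked | marked | marked | marked |

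The German ECG and vital-sign rows are also marked on Days 8 and 9, so the blanks belong to particular rows and not to the visits.

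**Step 2. Check the reading.** The German table printed with the Amendment 4 changes (Section 12.10.4) shows the same shape: four marks, two blanks, then marks again. That row does not line up cleanly with its own header, so it is supporting evidence only. The UK Day 8 mark rests on Section 7.1 alone. In that table the total IgE row is blank on Day 8, so the extracted text does separate blank from filled cells.

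**Step 3. Gaps between scheduled samples.**
- UK: 8 − 5 = 3 days, then 15 − 8 = 7 days.
- Germany: 15 − 5 = 10 days.

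Dosing is on Day 1, so 7–10 days post dose is study Days 8–11. Scheduled C3/C4 samples in that window: UK one (Day 8, its first day), Germany none.

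**Step 4. How far from peak are the neighbouring samples?** The protocol gives no absorption rate, so this step uses an assumed one-compartment model with first-order absorption:
- ke = ln 2 / 37 per day
- Tmax = ln(ka/ke)/(ka − ke), solved for ka
- C(t) proportional to exp(−ke·t) − exp(−ka·t)

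| Assumed Tmax (days) | ka (per day) | 72 h, % of Cmax | Day 5 (4 days post dose) | Day 8 (7 days) | Day 15 (14 days) |
|---|---|---|---|---|---|
| 7 | 0.483 | 84 | 93 | 100 | 91 |
| 8.5 | 0.370 | 76 | 86 | 99 | 94 |
| 10 | 0.294 | 69 | 80 | 97 | 97 |

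The range at 72 h (69–84%) brackets the protocol's figure of about 80%, so the model is a fair guide. On it, the German samples on Days 5 and 15 fall at 80–93% and 91–97% of Cmax.

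**Step 5. Participants affected.** Section 4.2 plans 6 active and 2 placebo in the 2, 10 and 300 mg cohorts, and 9 active and 3 placebo in the 30 and 100 mg cohorts. No country split is given. If no participant in a cohort is German, no Day 8 values are lost. If all are, the whole Day 8 cell (6 + 2 = 8 or 9 + 3 = 12 participants) is empty.

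**The case against.** The strongest objection concerns the evidence. The UK Day 8 mark appears in one printing of a table with visible extraction faults. The UK diary-review row starts at Day 15, although its footnote calls for review at every out-patient visit. The UK IL-5 row lacks marks at 24 h, 48 h, Day 5 and Day 57 that the German row has. If the Day 8 cell was misread, the country difference disappears. This stands as a reason to check the original table first. It does not remove the point, because the UK complement row fills every column of its header without a shift.

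The second objection is that little depends on the missing sample, and this largely stands. Haematology, chemistry, urinalysis and hsCRP are drawn on German Days 8 and 9. Sections 7.3 and 7.7 and Appendix 3 allow added or symptom-driven tests. The escalation rule in Section 4.3 needs at least 4 weeks of safety data from at least four active participants and 72 hours from the rest, so it does not turn on a Day 8 complement value. Section 9.1 plans no formal safety comparison.

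A reader might infer that the primary endpoint goes unmeasured in Germany around peak exposure, or that immune complex disease could not be detected there until Day 15. The documents do not support either reading. One visit is missing, the samples on either side are probably near peak, and complement is one of several markers listed for this risk. A reader might also take the progressive C3/C4 decrease in Section 5.4.2 as a laboratory trigger in its own right. It qualifies only the peripheral neuropathy item. Nor does the protocol link a complement fall to Tmax: in both tables circulating immune complexes go from 24 h to Day 15, and post-dose immunogenicity sampling starts at Day 15.

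**Conclusion.** The two schedules disagree and the protocol does not say why. The consequence is one missed C3/C4 sample per German participant, a 10-day interval in place of 3 and 7 days, and a Day 8 summary limited to UK participants. The effect is modest, and the correction is worth making mainly because it is so cheap. The conclusion rests on the UK Day 8 mark being confirmed in the original table and on some German enrolment in each cohort. The statement that Days 5 and 15 are close to peak rests on the assumed one-compartment model and the protocol's predicted half-life and Tmax.

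**What to change.** First check the UK Day 8 complement mark in Section 7.1 against the original table. If it is confirmed, reconcile the complement rows of Sections 7.1 and 12.8.2.1 so that C3/C4 is drawn at the same post-dose visits in both countries, using the German Day 8 draw already scheduled. Alternatively, state in Section 12.8.2 why the schedules differ.

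The cost is one extra aliquot per German participant at an existing in-patient draw, with no new visit. Section 7 lets time points be added by Note to File, so no amendment is needed for this alone.
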